## 8.2.2 Dosage Schedule

Givinostat oral suspension (10 mg/mL) and placebo oral suspension is to be administered orally as 2 oral doses daily in a fed condition (e.g. in the morning after breakfast and in the evening after dinner). Before its use, the suspension must be shaken for at least 30 seconds by rotating the bottle 180°. The suspension is administered by means of a graduated dosing syringe. The dosage to be administered is based on patient weight as described below:

Weight (kg) >30 and <40 >40 and <50 >50 and <60  $\geq$ 60 and < 70 >70 Dose (mg) bid 26.7 33.3 36.7 40 46.7 Oral suspension (mL) 2.7 4 3.3 3.7 4.7

Table 3: Givinostat-Placebo Starting Dose

## Dose Modifications:

After randomization, patients will be asked to have hematology assessments every two weeks during the first two months of treatment to closely monitor these parameters for safety purposes.

Study treatment dose adjustment including safety rules for permanently or temporarily stopping study treatment are described in Section 7.3.1.

As mentioned in Section 7.3.1, if a patient has consistent (at least 2 consecutive evaluations) platelet counts  $\leq 150 \times 10^9/L$  but does not meet the stopping criteria due to platelet reduction, the Investigator will have to reduce the dose by 20% of the current dose (See Table 4).

Study treatment can be resumed at a level 20% smaller than the dose at which an AE leading to a temporary stop occurred, once platelets and/or white blood cell and/or hemoglobin and/or triglycerides are normalized or when diarrhea is mild (See Table 4).

17 June 2020 Page 53 of 110

Table 4: Givinostat-Placebo Dose Modification

Starting Dose (mg) bid	26.7	33.3	36.7	40	46.7
Oral suspension (mL) bid	2.7	3.3	3.7	4	4.7
Reduced Dose (mg) bid	21.4	26.6	29.4	32	37.4
Oral suspension (mL) bid	2.1	2.7	2.9	3.2	3.7

## 8.3 Study Treatment Assignment

Patients will be dispensed the study treatment on an outpatient basis. All study treatment supplies are to be used only for this protocol and for no other purpose.

Patients will be assigned to one of the two treatment arms (givinostat vs. placebo) in a 2:1 ratio. The randomization process will be stratified by the factor related to concomitant steroid use at baseline (yes vs. no).

The randomization numbers will be generated using procedures that ensure that treatment assignment is unbiased. A patient randomization list will be produced using a validated system that automates the random assignment of patient numbers to randomization numbers.

At Visit 3, all patients who fulfill all inclusion criteria and none of the exclusion criteria will be randomized via an Interactive Web Response System (IWRS) to one of the treatment arms. The investigator or his/her delegate will log on to the IWRS, confirm that the patient fulfills all the inclusion/exclusion criteria and enter information relevant to the stratification factor. The IWRS will assign a randomization number to the patient which will be used to link the patient to a treatment arm.

During the study, the Investigator will supply the patient with the appropriate number of suspension bottles sufficient to cover the period between two visits (3 months of treatment).

The Investigator is to use the IWRS at each dispensing visit to obtain the packaging number of the study treatment to be dispensed to the patient. Study treatment should be dispensed by authorized personnel only.

The Investigator will provide the patient with written instructions on the dosage and corresponding volume in milliliters of suspension to be taken at each administration.

17 June 2020 Page 54 of 110

In the unlikely case of system unavailability, the Interactive Voice Response System (IVRS) will be used as backup for randomization and treatment assignment.

# 8.4 Blinding

This is a double-blind, placebo-controlled study, so patients receiving givinostat or placebo will receive medication indistinguishable in appearance. Personnel involved in the study (Investigators, nurses, all other site personnel, clinical research associate [CRA], Medical Monitors, Project Managers, Data Managers and Statisticians) will remain blind at all times, unless knowledge of the study treatment is relevant to the safety of the patient. If the Investigator or authorized designee decides to break the code of a patient, it is suggested that the Monitoring Team (Medical Monitor or CRA) be consulted if possible before breaking the code, however this is not mandatory since the decision of the Investigator cannot be influenced nor does it require the approval of the Monitoring Team.

Code breaking can be performed by the Investigator or authorized designee at any time by using the proper module of the IWRS. In the unlikely case of system unavailability, the Interactive Voice Response System (IVRS) will be used as backup for code breaking.

If the code is broken the Investigator must record the date, time, and reason for breaking the code in the eCRF, and must notify the Monitoring Team as soon as possible.

Before withdrawing a patient, each case can be discussed with the study medical monitor, but the final decision remains with the Investigator only or authorized designee. If the safety of the subject can be reasonably assured, the subject will not be discontinued.

As platelet count reductions are observed after treatment with givinostat, study site personnel who perform the histology analysis, the functional tests and the MRI/MRS analysis must be different from the personnel who review safety results and these must not be shared with the personnel responsible for the functional tests, histology and MRI/MRS analyses.

Regarding the PK results, all the personnel involved in the study will remain blind at all times and Sponsor may review the PK results only in scrambled format.

17 June 2020 Page 55 of 110

## 8.5 Drug Supply

The investigational site will be supplied with a number of suspension bottles sufficient to treat the patients enrolled in the study.

## 8.5.1 Packaging

Primary packaging will consist of an amber plastic bottle containing the suspension. Givinostat/placebo oral suspension is supplied in a 150 mL capacity amber PET bottle closed by means of a red-white HDPE child-proof screw cap with a LDPE shutter/syringe-adapter. Each bottle contains 140 mL of givinostat 10 mg/mL or placebo. The secondary packaging will be a carton box containing one amber bottle and two syringes as dosing systems for dispensing the suspension.

## 8.5.2 Labelling

The primary and secondary labels will show all the information requested in accordance with Annex 13 of Good Manufacturing Practice and local legislation.

Medication labels will be in the local language.

The labels will include at least:

- Name of the medicinal product
- Pharmaceutical dosage form
- Route of administration
- Quantity of dosage units
- Strength/potency
- Batch number/Packaging number
- Sponsor's study code (\*)
- EudraCT number (\*)
- Investigator name (\*)
- Site and patient number (\*)
- Treatment/Randomization number (\*)
- Name, address, and telephone number of the main contact (the sponsor or the contract research organization or the investigator) (\*) (\*\*)
- Period of use (\*)
- Storage conditions (\*)
- Directions for use (\*) (\*\*)
- For clinical trial use only (\*)

17 June 2020 Page 56 of 110

Keep out of reach of children (\*)

### Notes:

- (\*) According to Annex 13 and EU law in force, when using a centralized electronic randomization system, some of the listed information may be omitted from the label.
- (\*\*) According to Annex 13, such information might not need to appear on the label if separately provided in a leaflet or card.

## 8.5.3 Storage

The investigational site will store the study treatment under the conditions specified here below, ensuring that it is not accessible to unauthorized persons until it is dispensed to the patient.

Givinostat/placebo suspension is to be stored in a refrigerator at  $5^{\circ}$ C  $\pm$   $3^{\circ}$ C. Once the container is opened, the suspension can be administered for a maximum of 30 days.

## 8.6 Treatment Accountability and Compliance

The study treatment packaging will be provided with tear-off labels; before treatment dispensation the tear-off label should be removed from the patient's pack by the Investigator and stuck on the appropriate drug accountability form.

At each dispensing visit, the patient will return all bottles previously received (used, partially used and unused) and receive a new supply of the study treatment.

Patient compliance will be evaluated through a patient diary indicating how many doses were effectively administered by the patient.

Drug accountability will be checked by Italfarmaco S.p.A. or its designee based on an accountability log completed by site staff and monitored by Italfarmaco S.p.A. or its designee.

The used, partially used, and unused bottles will be collected and sent back to Italfarmaco S.p.A. or their designee periodically or at the end of the study.

17 June 2020 Page 57 of 110

#### 8.7 Prior and Concomitant Illnesses and Medications

### 8.7.1 Prior and Concomitant Illnesses

Investigators should document all significant prior illnesses that the patient has experienced within 6 months of screening. Additional illnesses present at the time when informed consent is given and up to the time of first dosing are to be regarded as concomitant illnesses.

Illnesses first occurring or detected during the study and/or worsening of a concomitant illness during the study are to be documented as AEs on the eCRF.

### 8.7.2 Prior and Concomitant Medications

All medications and other treatments taken by the patient during the study, including those treatments initiated within 6 months prior to the start of the study, must be recorded on the eCRF.

Concomitant treatments are defined as treatments taken after study treatment administration. Any medication or therapy that is taken by or administered to the patient during the study must be recorded in the eCRF. The entry must include dose, regimen, route, indication, and dates of use.

After the Screening visit, medication to treat minor treatment-emergent illnesses are generally permitted; supportive treatments such as antiemetics, antidiarrheals, antipyretics, anti-allergics, analgesics and antibiotics are allowed.

Use of Vitamin D, calcium and any other supplements if clinically indicated before enrollment and for the duration of the study is allowed

The following therapies are expressly prohibited throughout the study:

- Any other investigational drug while on this study.
- Any dystrophin restoration product.
- Any pharmacologic treatment, other than corticosteroids, that might have an effect on muscle strength or function (e.g., growth hormone).

The following are concomitant therapy requiring caution throughout the study:

 Drugs known to increase the QT interval (see Appendix 16.1 for a list of such compounds).

17 June 2020 Page 58 of 110

- Live or live attenuated vaccines: the patient must be carefully monitored. While the
  decision of the Investigator cannot be influenced, rejected nor approved by the
  Medical Monitor, it is advised but not mandatory that the Investigator discuss the case
  with the Medical Monitor before using these vaccines.
- Drugs known to be a substrate of Organic Cation Transporter 2 (see Appendix 16.2 for a list of such compounds).
- Antiplatelet, thrombolytic or anticoagulant drugs must be carefully monitored.
- Drugs known to be P-glycoprotein inhibitors (see Appendix 16.3 for a list of such compounds).

## 8.8 Treatment for hypertriglyceridemia

If a subject experiences an increase of triglycerides >ULN during the study, the investigator is allowed to prescribe adequate treatment including dietary supplements. These treatments will be reimbursed by the Sponsor.

### 9 STUDY PROCEDURES

Table 5 outlines the timing of procedures and assessments to be performed throughout the study. See Section 9.1 for additional details of study procedures.

17 June 2020 Page 59 of 110

Table 5: Schedule of Assessments

Month	-1 -4		0	1		2		3	6	9	12	13
Week			0	2 4		6	8	12	24	36	48	52
Visit window	+ 2 weeks		0	± 3 days	± 3 days	±3 days	± 3 days	± 7 days	± 7 days	± 7 days	± 7 days	± 7 days
	Vl	V2	V3	V4	V5	V6	V7	V8	V9	V10	V11	V12
Visit*	Screening		Rand								EOS/Early Withdrawal 	FUV 
Informed consent	X											
Eligibility criteria	X											
Medical history and demographic data	X											
Prior and concomitant medications	Х		X	Х	X		X	X	X	X	Х	x
Physical examination	X		X	X	X		X	X	X	X	X	X
Vital Signs	X		X	X	X		X	X	X	X	X	X
Weight	X		X	X	X		X	X	X	X	X	
Height	X										X	
ECG Test 	X		X	X	X		X	X	X	X	X	X
ЕСНО	X										X	
Pulmonary function tests 	X										X	
Serology 	X											
Hematology 	X		X	X	X	X	X	X	X	X	X	X
Blood chemistry 	X						X	X	X	X	X	X
Thyroid function tests (TSH, fT3, fT4)	X				x		x	x	X	X	X	x
Coagulation tests (PT and aPTT)	X						X	X	X	X	X	X
Urine analysis 	X						X	X	X	X	X	X
SF-36	X		1								X	
Time function tests (time to climb 4 standard steps, time to rise from floor, time to walk 10 m)	х							х	х	х	x	

17 June 2020 Page 60 of 110

Month	-1		0	1		2		3	6	9	12	13
Week	-4		0	2	4	6	8	12	24	36	48	52
Visit window	+ 2 weeks		0	± 3 days	± 3 days	±3 days	± 3 days	± 7 days	±7 days	± 7 days	± 7 days	± 7 days
	Vl	V2	V3	V4	V5	V6	V7	V8	V9	V10	V11	V12
Visit*	Screening		Rand								EOS/Early Withdrawal 	FUV 
6MWT	X		X					X	X	X	X	
MFM	X							X	X	X	X	
Muscle strength 	X							X	X	X	X	
PK blood sample collection 					X			X	X		X	
Biomarkers blood collection 			X						X		X	
Study treatment dispensation and accountability			Х					X	X	X		
Patient diary dispensation			X									
Patient compliance through diary								X	X	X	X	
AE assessment	X	X	X	X	X	X	X	X	X	X	X	X
MR + Muscular biopsy		$X^{11}$									$X^{13}$	

6MWT=6-minute walking test; AE=adverse event; MFM= Motor Function measure; SF36= Short Form (36) Health Survey; PT=Prothrombin time; aPPT= activated partial thromboplastin time; ECG= electrocardiogram; ECHO= echocardiogram; PK= pharmacokinetics; MRI= magnetic resonance imaging; FEV1= forced expiratory volume at 1 second; FVC=forced vital capacity; PEF= peak expiratory flow; RBC-red blood cell; WBC=white blood cell; ALT=alanine aminotransferase; AST=aspartate aminotransferase; LDH= lactate dehydrogenase; CRP=C-reactive protein; GGT=gamma-glutamyl transpeptidase; BUN=blood urea nitrogen; fT3= free T3 (the active part of triiodothyronine); fT4=Free T4 (the active part of thyroxine); TSH=thyroid-stimulating hormone; eGFR=estimate Glomerular Filtration Rate; HHM=hand-held myometry; MMT=manual muscle testing

- \* Unscheduled visits may take place at the discretion of the Investigator such as additional cardiology visits at the study center or visits at the patient's home by a qualified trained nurse for blood sample collection.
- If the patient is discontinued from the study treatment, the patient will be asked to return for the early withdrawal visit to be performed within 4 weeks
  of the last dose of study treatment. In this case, the SF-36 evaluation and MRI may not be performed.
- The patients who complete the study (i.e. 12 months of treatment) will be asked to return to the centre for the Follow-up visit to be performed after 4
  weeks from the last dose of study treatment (i.e. 4 weeks ±1).
- 3. A 12-lead ECG is to be done in triplicate at the screening visit and during the other visits if an ECG demonstrates a prolonged QTcF interval > 450 msec obtained on 2 more ECGs over a brief period. The averaged QTcF values of the 3 ECGs is to be used to determine whether the patients should be discontinued from the study.
- Pulmonary function tests: FEV1, FVC and PEF.
- Serology CMV IgM, HBsAg/HCV/HIV, EBV IgG.

17 June 2020 Page 61 of 110

- 6. Hematology test: RBC, WBC (including differential count), hemoglobin, MCH, MCHC, MCV, hematocrit, and platelets. Test will be done according to the schedule (i.e., every two weeks the first 2 months of treatment) and are to be performed more frequently if clinically indicated. Note: Repeat visits for the platelets count will be performed at the request of the Investigator.
- Serum blood chemistry: total bilirubin, direct bilirubin, alkaline phosphatase, amylase, ALT, AST, LDH, cystatin C, CRP, GGT, creatine kinase, total
  protein, albumin, uric acid, triglycerides, phosphorus, total cholesterol, LDL, HDL, sodium, potassium, chloride, calcium, glucose, creatinine, BUN,
  bicarbonate), NT-proBNP.
- Urinalysis: appearance, pH, specific gravity, protein, glucose, ketone bodies, blood and WBCs, and urobilinogen.
- Muscle strength tests: knee extension, elbow flexion by HHM.
- 10. Pharmacokinetic sample collection: sampling (2 pre-dose during the treatment and 4 post-dose) will be collected as described in the protocol during the following visits: 5 (4 weeks), 8 (12 weeks), 9 (24 weeks), and 11 (Week 48). At these visits, the patient will be asked to take the morning dose at site.
- 11. The first MRI (by Dixon technique), MRS tests and muscular biopsy have to be performed when all inclusion/exclusion criteria have been already evaluated and the patient is eligible. MRI/MRS and muscular biopsy can be performed in different days.
- 12 LTBP4 and osteopontin genotype after randomization and blood sample collection for serum circulating proteins (by an ELISA based system) at randomization, 6 months and at the end of treatment.
- 13 MRI/MRS and biopsy may be performed on different days. Treatment is to continue up to the last assessment.

17 June 2020 Page 62 of 110

# 9.1 Procedures by Study Visit

Twelve (12) study visits, including the Screening and Randomization Visits, are planned. Assessments will be performed as outlined in the following by-visit subsections. As platelet count reductions are observed after treatment with givinostat, study site personnel who perform functional tests and MRI/MRS must be different from the personnel who review safety results related to laboratory tests, and these must not be shared with the personnel responsible for the functional tests and MRI/MRS.

## 9.1.1 Visit 1 and Visit 2 - Screening (Week -4 + 2 weeks)

The Screening visits (Visit 1 and Visit 2) will occur within 4 weeks (± 2 weeks) prior to the Randomization Visit. The following assessments will be performed at Visit 1:

- Written Informed Consent
- Eligibility criteria: review of inclusion and exclusion criteria
- Medical history and demographic data
- Prior medications (taken in the past 6 months)
- Physical examination
- Vital signs (blood pressure, heart rate and body temperature)
- Weight and height
- 12-lead ECG (in triplicate)
- Echocardiogram
- Pulmonary function tests: FEV1, FVC, FEV1/FVC, and PEF
- Blood collection for:
  - serology
  - hematology
  - blood chemistry
  - coagulation tests (prothrombin time [PT] and activated partial thromboplastin time [aPTT])
  - thyroid function tests (TSH, fT3, fT4)
- Urine analysis
- Quality of Life test (SF-36)
- 6MWT + MFM
- Muscle strength test (knee extension and elbow flexion by HHM)
- Time function tests
- AE assessments

17 June 2020 Page 63 of 110

If all inclusion and exclusion criteria have been met and the patient is eligible, an MRI, MRS and muscle biopsy are to be performed before the first IMP dose. At the discretion of the Investigator, patients not meeting inclusion/exclusion criteria may be re-screened twice with an interval of at least 30 days between assessments.

At Visit 1, after having filled in the "Eligibility criteria" section of the eCRF, eligible patients will be randomized to one of the two following muscle biopsy sequences by the system:

V2: Right Arm - V11: Left Arm

V2: Left Arm - V11: Right Arm

The site will receive the muscle biopsy sequence by email.

Randomization will be balanced in a ratio of 1:1 and will not be stratified.

If needed for logistic reasons, Visit 2 can be completed on two different days included in the window period between Visit 1 and Visit 3. Patients will be instructed to avoid physical activity that would exceed their normal activity for 3 days before each visit.

# 9.1.2 Visit 3 - Randomization (Week 0)

Data collected at Visit 3 will represent baseline values for study endpoints.

At Visit 3, the following assessments will be performed:

- Review of eligibility criteria using the assessments done at screening.
- Prior and concomitant medications
- Physical examination
- Vital signs (blood pressure, heart rate and body temperature)
- Weight
- 12-lead ECG
- Blood collection for hematology and biomarker evaluation
- 6MWT
- Randomization and dispensation of study treatment
- AE assessments
- Patient diary dispensation

### 9.1.3 Visit 4 (Week 2 ± 3 days)

The following assessments will be performed at Visit 4, after 2 weeks (± 3 days) of treatment:

17 June 2020 Page 64 of 110

- Concomitant medications
- Physical examination
- Vital signs (blood pressure, heart rate and body temperature)
- Weight
- 12-lead ECG
- Blood collection for hematology
- AEs assessments

## 9.1.4 Visits 5 (Week $4 \pm 3$ days)

The following assessments will be performed at Visit 5, after 4 weeks (± 3 days) of treatment. Patients will be instructed to take the morning dose at the site in case of pre-dose PK analysis.

- Concomitant medications
- Physical examination
- Vital signs (blood pressure, heart rate and body temperature)
- Weight
- 12-lead ECG
- Blood collection for hematology, thyroid function tests (TSH, fT3, fT4) and PK analysis

AEs assessments

### 9.1.5 Visit 6 (Week 6 ± 3 days)

Visit 6 is required if the platelet values at any visit during the first month of treatment decreased more than 10% from the PLT value measured at the Randomization Visit (i.e. Visit 3-week 0) or at the discretion of the Investigator.

Visits 6 will be performed 6 weeks after the Randomization Visit (± 3 days) essentially for safety purposes, and the following assessments will be performed:

- Blood collection for hematology
- AE assessments.

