\* Based on average QTc value of triplicate ECGs. For example, if an ECG demonstrates a prolonged QT interval, 2 more ECGs should be obtained over a brief period, and then the averaged QTcF values of the 3 ECGs should be used to determine whether the patient should be discontinued from the study. If the mean QTcF value of the 3 replicates still meets the stopping criteria, the patient has to interrupt the study treatment, the medical monitor has to be informed and the value must be confirmed by central reading before withdrawing the patient from the study. The QTc has to be calculated with the Fridericia formula QTc = QT/RR1/3.

The Study treatment should be temporarily interrupted if any of the following events occur:

- Moderate or severe diarrhea (increase more than 4 stools per day).
- Platelet count < 75 x 10^9/L but > 50 x 10^9/L (treatment should be temporarily stopped, and the platelet count repeated within 1 week and retested until platelets are normal).
- White blood cell < 3.0 x 10^9/L but > 2.0 x 10^9/L (treatment should be temporarily stopped, and white blood cells re-measured within 1 week and retested until white blood cells are normal).
- Hemoglobin < 10.0 g/dL but > 8.0 g/dL (treatment should be temporarily stopped, and hemoglobin re-measured within 1 week and retested until hemoglobin is normal).
- Triglycerides > 300mg/dL (see also section 8.8)

The study treatment can be reduced by 20% of the current dose at which the AE leading to temporary interruption occurred, once platelets and/or white blood cell and/or hemoglobin and/or triglycerides are normalized, or diarrhea is mild. See Section 8.2.2 for more details.

The patient may have unscheduled visits if needed until the AE resolves, and will then continue the study as per scheduled visits. Further procedures (blood sample collection) may also be performed by a qualified trained nurse at the patient's home.

17 June 2020 Page 49 of 110

In addition, if a patient has a consistent (at least two consecutive evaluations) platelet count  $\leq$  150 x 10^9/L that does not meet stopping criteria for platelets, the Investigator will have to reduce the dose by 20% of the current dose. See Section 8.2.2 for more details.

Hematology parameters will be evaluated every 2 weeks during the first 2 months of treatment (Visits 4-7) to closely monitor these safety parameters.

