6.4.4. Laboratory parameters

The absolute value and change from baseline will be analyzed for each laboratory parameters separately for hematology, biochemistry, coagulation, serology and urinalysis by means of summary descriptive statistics at each time point, by treatment group. In addition, shift tables using the low/normal/high classification to compare baseline to the worst ontreatment value will be provided.

Listings of all laboratory data with values out of range will also be provided.

In addition, the following summaries in relation to post-baseline platelet counts will be presented by treatment group: minimum values, time to nadir (days) and time to recovery (days). These will be defined as follows:

Minimum value = minimum post-baseline platelet count for the subject.

Time to nadir (days) = time from the date of first drug administration to first minimum post-baseline value regardless if this is within the normal range.

Time to recovery (days) = for subjects whose minimum post-baseline value is below the lower limit of normal, the time to recovery is calculated as the time from the minimum value below lower limit of normal to the first value within the normal range.

Furthermore, the above summaries will be repeated for patients who reduced dose at least once due to platelet count decrease. Moreover, for this subgroup of patients, the following variables will be described as well:

- time on treatment after recovery (days), additional platelet decrease after recovery, time on treatment without recovery (days), where:
- time on treatment after recovery = for subjects who record recovery from the minimum value below the lower limit of normal, the time on treatment after recovery is calculated as the time from the date of recovery to the last treatment date or date of data cut-off.
- additional platelet decrease after recovery = number of subjects who record recovery from the minimum value below the lower limit of normal and then record a subsequent value below the lower limit of normal.
- time on treatment without recovery = for subjects who do not record recovery from
 the minimum value below the lower limit of normal, the time on treatment without
 recovery is calculated from the date of the minimum value below the lower limit of
 normal to the last treatment date.

Sponsor: ITALFARMACO
Protocol: DSC/15/2357/53

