A box-plot will be produced for the following parameters over time by treatment group: platelets, hemoglobin, neutrophils, leukocytes, triglycerides and total cholesterol.

Pharmacokinetics

Finally, pharmacokinetic parameters (ITF2374 and ITF2375) for patients treated with givinostat will be listed by patient together with the IMP dosage. Further details will be provided in a separate SAP.

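### If Visit 6 is taken as Protocol 9.1.5 words it, the by-arm Week-6 platelet change rests on patients selected by an earlier fall; the protocol contradicts itself on who is sampled, and the SAP has no rule for it

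*Protocol*

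**What the plan says.** **Who has Week-6 blood taken.** Protocol 9.1.5 makes the visit conditional: "Visit 6 is required if the platelet values at any visit during the first month of treatment decreased more than 10" per cent from the count at the Randomization Visit (Visit 3), "or at the discretion of the Investigator".

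Other places set no condition:
- Protocol 7.3.1: "Hematology parameters will be evaluated every 2 weeks during the first 2 months of treatment (Visits 4-7) to closely monitor these safety parameters".
- Protocol 8.2.2, Dose Modifications: "patients will be asked to have hematology assessments every two weeks during the first two months of treatment".
- Protocol Table 5 marks haematology at Visit 6 like any other visit, and its footnote 6 reads "Test will be done according to the schedule (i.e., every two weeks the first 2 months of treatment".

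**How the values are summarised.** SAP 6.4.4 presents absolute value and change from baseline "by means of summary descriptive statistics at each time point, by treatment group", and adds "A box-plot will be produced for the following parameters over time by treatment group: platelets, hemoglobin, neutrophils, leukocytes, triglycerides and total cholesterol". It makes no exception for Visit 6. SAP 4.2 takes the last pre-dose value as baseline, which for haematology is normally Visit 3. SAP 6.4 applies no missing-data method to safety parameters. SAP 6.4.4 also reports each patient's minimum platelet count, time to nadir, time to recovery and shift to the worst on-treatment value.

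**The concern.** Under 9.1.5 a patient has a Week-6 value mainly because his Week-2 or Week-4 count was more than 10% below his Visit 3 count. The Week-6 change is measured from that same Visit 3 count. A placebo patient with stable platelets meets the trigger largely when Visit 3 was high by chance. His Week-6 change is then negative without any drug effect.

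The Week-6 column would stand beside Weeks 2, 4, 8 and 12, which are scheduled for every patient, and nothing would mark the difference. Platelet reduction is the best-documented toxicity of this drug, and readers use the by-visit table to follow its time course. They could see a fall on placebo at Week 6 that is absent at the neighbouring visits, and a gap between the arms that reflects who was sampled.

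**Working it through.** The documents give no figure for the Week-6 platelet contrast, so there is none to reproduce. The size was found by simulation, with 400,000 patients per arm and scenario.

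**Inputs from the documents**
- Trigger: Week-2 or Week-4 count below 0.9 × Visit 3 count (9.1.5).
- Baseline: Visit 3 count (SAP 4.2).
- Planned placebo arm: 17 (Protocol 13.1).

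**Assumptions (not in the documents)**
- True platelet level centred on 240 × 10⁹/L.
- Log-normal visit error with CV 5%, 8% or 12%; correlation between two-week neighbours 0 or 0.5.
- No true change on placebo.
- Mean givinostat fall 10-40%, with a between-patient SD of 10 points.
- Share of untriggered patients seen at discretion: 0 or 30%.

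**Step 1. Placebo, mean percentage change at Week 6, CV 8-12%**

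| Patients seen | Share triggered | Mean change |
|---|---|---|
| Triggered only, independent visits | 28-40% | -6.7% to -7.5% |
| Triggered only, correlation 0.5 | 19-32% | -9.0% to -9.9% |
| Triggered plus 30% of the rest | as above | about -2% to -3.5% |

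For all placebo patients with independent visits, the mean percentage change is slightly positive, because the denominator is noisy: exp(0.08²) - 1 = 0.6% to exp(0.12²) - 1 = 1.5%. On 17 placebo patients, 19-40% is 0.19 × 17 = 3.2 to 0.40 × 17 = 6.8, or about 3 to 7 men.

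**Step 2. Check on the effect of discretionary visits** (CV 8%, independent visits, units 10⁹/L). Triggered placebo patients (28%) average -18.4. The mean over everyone is 0, so the untriggered average 18.4 × 0.28/0.72 = +7.2. Adding 30% of the untriggered (0.30 × 0.72 = 0.216) gives (0.28 × -18.4 + 0.216 × 7.2)/(0.28 + 0.216) = -7.3, which matches the simulated value.

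**Step 3. Arm difference in mean change** (CV 8%, units 10⁹/L; percentage of the true difference in brackets)

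| Mean drug fall | All patients, about | Trigger only, corr. 0 | Trigger only, corr. 0.5 | Plus 30%, corr. 0 |
|---|---|---|---|---|
| 10% | -25 | -23.4 (95%) | -19.1 (78%) | -27.3 (111%) |
| 20% | -49 | -38.4 (78%) | -32.6 (66%) | -46.9 (95%) |
| 30% | -74 | -57.5 (78%) | -51.4 (70%) | -67.9 (92%) |
| 40% | -98 | -80.4 (82%) | -74.2 (75%) | -91.4 (93%) |

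Worked cell: for a 30% fall, trigger only, independent visits, the arm means are -76.0 and -18.5. The difference is -57.5 against -73.6, and 57.5/73.6 = 78%.

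Over all CVs and both correlations:
- Trigger only: 64-84% of the truth for falls of 20-40%, and 71-104% for a 10% fall.
- With 30% of the untriggered also seen: 87-104% and 102-133% respectively.

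The direction changes because, with a small drug effect, only 57-65% of givinostat patients are triggered, so selection deepens that arm's mean too.

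**Step 4. Absolute values.** With independent visits the placebo Week-6 mean is not shifted: one run at CV 10% gave 241.1 in triggered patients and 241.1 in all. For a 30% fall at CV 8%, trigger only, the arm difference in absolute values is -75.2 against -73.7. With correlation 0.5 it is -68.0 against -73.7, or 68.0/73.7 = 92%.

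**The case against.** The strongest reply is that most of the protocol calls for Week-6 haematology in everyone. Sections 7.3.1 and 8.2.2, Table 5 and its footnote 6 set no condition, and Protocol 6.1 has visits every two weeks in the first two months. If sites did that, there is no selection and the SAP summary is sound. This stands, and it is why the point is conditional. It does not dispose of the matter: 9.1.5 is the one section that states when Visit 6 is required, and nothing says which text prevails.

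The second reply is that little rests on Week 6. Protocol 4.2.2 puts the platelet nadir at 2 to 3 weeks, followed by a plateau. Weeks 2 and 4 bracket the nadir, and Weeks 8 and 12 cover the plateau. The patient-level minimum, nadir and worst-value shift do not depend on the Week-6 mean. No between-arm laboratory test or estimate is planned, and Protocol 13.3 reports the number of patients at each visit by arm, so a shortfall would be visible. All of this stands and limits the severity. A count of attenders does not, however, tell the reader that they were chosen by an earlier platelet fall.

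A reader might infer more than the documents support:
- **That the drug effect is understated as a rule.** Step 3 shows that the bias can vanish or reverse, and the documents give no rate of discretionary visits. The sponsor's blinded estimate in Amendment 2, that about 80% of givinostat patients (11/14) needed a dose reduction, makes a sizeable effect plausible, but it comes from the earlier, higher starting dose.
- **That the box-plots show a false placebo dip.** SAP 6.4.4 does not say that they plot change from baseline. Absolute values shift on placebo only if platelet deviations persist between visits.
- **That the other haematology parameters are biased.** They would come from the same subset, but the selection is on platelets, and no bias in them has been shown.

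**Conclusion.** The point holds as a contradiction in the protocol together with a conditional flaw in the SAP. If 9.1.5 governs, the Week-6 change from baseline by arm describes an outcome-selected subset, and the placebo mean is negative by selection. At assumed CVs of 8-12%, it is about -7% to -10% with triggered patients only, and about -2% to -3.5% if 30% of the others are also seen. The Week-6 arm difference in change is distorted in a direction that depends on the size of the drug effect and on how often investigators use their discretion.

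These sizes rest on assumed variability, correlation, drug effect and discretion rate, none of which the documents give. If every patient has Week-6 haematology, the bias is zero. Severity is minor: one descriptive time point, mainly its change-from-baseline column.

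**What to change.** 1. **Protocol.** Reconcile 9.1.5 with 7.3.1, 8.2.2, Table 5 and footnote 6 on who has Visit 6 haematology. Which rule applies is for the sponsor to decide.
2. **SAP 6.4.4.** State that, unless Week-6 counts exist for essentially all patients in both arms:
   - Visit 6 haematology is listed as triggered or unscheduled, with N and the reason (platelet trigger or discretion) per arm;
   - it is left out of the by-arm change-from-baseline tables and the over-time box-plots;
   - arms are compared over Visits 4, 5, 7 and 8.
3. **Keep** Visit 6 values in the patient-level minimum, nadir and worst-value shift summaries.

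The SAP cost is wording and, if Visit 6 proves incomplete, one fewer column in descriptive tables. The protocol cost is a clarification of existing text.
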